A Cochrane systematic review published in 2017 (12) analyzed 41 randomized controlled trials of 4,206 adults who received non-depolarizing NMBAs for elective surgery, and found that a 2 mg/kg dose of sugammadex was 6.6 times faster (10.22 minutes) than a 0.05 mg/kg dose of neostigmine in reversing moderate NMB from the second twitch (T2) to a TOF ratio > 0.9, while

_

¹ The ratio of the fourth (T4) to the first (T1) twitch after a TOF stimulation

a 4 mg/kg dose of sugammadex was 16.8 times faster (45.78 minutes) than a 0.07 mg/kg dose of neostigmine in reversing deep NMB from a PTC 1-5 to TOF ratio > 0.9.

However, less is known when there is shallow NMB, i.e. when the TOF count is 4 but there is still detectable TOF fade. Concerningly, Kirkegaard *et al.* found in 2002 that the maximal 0.07 mg/kg dose of neostigmine was unable to reverse all patients to a TOF ratio of 0.9 within 30 minutes, even at a pre-intervention TOF count of 4 (13). Whether a lower dose of sugammadex would be sufficient to achieve a TOF ratio of 0.9 after shallow NMB has been examined by Schaller *et al.* in 2010 and Pongrácz *et al.* in 2013. The former group found that in a group of 94 adults undergoing elective surgery, a dose of 0.22 mg/kg of sugammadex was equivalent to a dose of 0.034 mg/kg of neostigmine in reversing NMB from a TOF ratio of 0.5 to 0.9 within 5 minutes in 95% of their patients (14). Conversely, Pongrácz's group found that a 0.5 mg/kg dose of sugammadex reversed NMB from a TOF count of 4 to a TOF ratio of 1.0 in 4.1 minutes on average compared to 2.1 minutes for a 1.0 mg/kg dose of sugammadex, 1.8 minutes for a 2.0 mg/kg of sugammadex, and 8.5 minutes for a 0.05 mg/kg dose of neostigmine (15).

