Due to the high cost of sugammadex, some researchers have hypothesized that a lower dose is required when combined with neostigmine. A 2015 study from Beirut in adults undergoing elective surgery demonstrated that a dose of 2 mg/kg of sugammadex combined with neostigmine 0.05 mg/kg was non-inferior to the standard dose of 4 mg/kg of sugammadex in reversing deep NMB, defined as returning from a TOF count of 0 to a TOF ratio of 0.9 within 5 minutes, with similar times to extubation as well as no cases of recurarization in the post anesthetic care unit (PACU) (16). Lobaz, Sammut and Damodaran reported in 2013 the use of sugammadex as rescue therapy for a 71-year-old patient with end stage renal disease who was unable to be weaned off the ventilator almost five hours after receiving a single 1.2 mg/kg dose of rocuronium. He had initially achieved a TOF of 4, was reversed with 2.5 mg of neostigmine 45 minutes after induction, but failed to maintain adequate spontaneous ventilation despite his TOF remaining at 4, and was transferred to the intensive care unit 3 hours post induction. There, his TOF steadily declined to 2, as a result of which he received a 6 mg/kg dose of sugammadex, causing him to be successfully extubated ten minutes later (17). It is similarly important to dose sugammadex appropriately; Carollo et al. published a case report in 2019 of an 8-month-old patient who had recurarization after a 4 mg/kg dose of sugammadex was given with a TOF count of 2/4, which fortunately resolved after a second 4 mg/kg dose of sugammadex (18).

Lastly, known common adverse effects of neostigmine include bradycardia, nausea and vomiting (19), while the use of sugammadex has been found to lead to nausea, vomiting, hypotension and headache in \geq 10% of patients (5). There have also been case reports of marked bradycardia possibly leading to cardiac arrest with the use of both agents.

Page 6 of 30 Version: 3 (10/14/2024)

4. Study Endpoints

Primary study outcome:

The time taken to achieve a TOF ratio of 0.9 after the use of the intervention drug versus placebo in a patient population that has already received neostigmine for NMB reversal.

Secondary study outcome:

The percentage of patients who achieve a TOF ratio of 0.9 within 1 minute, 2 minutes, 5 minutes, and 10 minutes.

Safety outcomes:

The incidence in PACU (measured in %) of:

- i. Nausea,
- ii. Vomiting,
- iii. Bradycardia²,
- iv. Tachycardia³, and
- v. Hypotension⁴.

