These patients will be randomized using the Emory University REDCap (Research Electronic Data Capture) software to six groups: 2 mg/kg (the lowest dose approved by the FDA), 1 mg/kg, 0.5 mg/kg, 0.25 mg/kg, 0.125 mg/kg of sugammadex and placebo. Doses would be based on actual body weight. The time taken to reach a TOF ratio of 0.9 thereafter would be measured. If the patient fails to achieve this goal by 10 minutes, sugammadex would be given in 2 mg/kg increments until the patient reaches this threshold and can be safely extubated. The TOF ratio would be measured again at 30 minutes after arrival at the PACU to exclude delayed residual NMB with the plan to give further 2 mg/kg doses of sugammadex if detected.

The inclusion of a placebo group would allow us to examine if patients may recover spontaneously over that time without needing any sugammadex at all, and what parameters may predict that subset of patients. It will also improve the dose response modelling, in that randomization has been weighted so that patients who are least likely to need sugammadex (i.e. if they achieved a TOF count of 4 twitches without fade) are more likely to be in the placebo group or at the lowest dose of sugammadex that is being tested.

The time taken to a TOF ratio of 0.9 after the intervention drug has been given would be compared for statistically significant differences, controlling for the:

- TOF count (3 twitches, 4 twitches with fade, 4 twitches without fade), and
- TOF ratio (0 to < 0.9)

15 minutes after neostigmine has been given and prior to giving the intervention drug.

Quantitative neuromuscular monitoring will be carried out using electromyography, which measures the TOF ratio every 20 seconds. The TOF count (between 0 to 4) and the TOF ratio (0 to 1) would be measured and recorded at baseline and after administration of the study drug. If the TOF ratio remains < 0.9 after this, or if the patient exhibits any symptoms or signs of residual NMB blockade, a further 2 mg/kg dose of sugammadex would be given until the patient achieves a TOF ratio of 0.9.

Page 8 of 30 Version: 3 (10/14/2024)

7. Statistical Analysis Plan

Power Analysis

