Assuming assumptions are valid, an increasing exponential regression model with random intercept will be fitted with Time of Four Ratio versus Time, stratified by the natural log of the five dose levels (modeled below). This translates to a slow response initially followed by a more rapid response later. The random intercept will allow for different initial TOFR values.

Page 9 of 30 Version: 3 (10/14/2024)

$$TOFR = \frac{1}{B}e^{(A+time)/B} + TOFR_{initial} + C * \ln(dose)$$

"Success" will be defined as TOFR of ≥0.9 within 5 minutes for 95% of patients, following the model estimate, adjusting for the 95% confidence intervals of the estimates, based on initial TOF ratios, which may be grouped as needed. A secondary analysis will be conducted by TOFC to determine optimal dose at each TOFC level, and if TOFC correlates strongly with TOFR.

8. Data and/or Specimen Banking

N/A

9. Sharing of Results with Participants

N/A

10. Study Timelines

All subjects are anticipated to participate in the study from the start of their surgery to the time of their discharge from the PACU, which should be on the same day. It is expected that 1 year would be required to enroll all study subjects, and for the study to be completed by July 2023.

11. Inclusion and Exclusion Criteria

Individuals will be screened for eligibility at the anesthesia pre-admission clinic.

Inclusion criteria:

- Patients aged 18 years and above who will
- Undergo an elective surgery in the main operating room or outpatient surgery center at Grady Memorial Hospital,
- Receive general anesthesia (standardized to sevoflurane for maintenance),
- Receive rocuronium for NMB,
- Receive neostigmine for NMB reversal,
- Achieve a TOF count of at least 3 twitches but not a TOF ratio of 0.9 fifteen minutes after neostigmine has been given, and
- Able and willing to provide informed consent.

Exclusion criteria:

Page 10 of 30 Version: 3 (10/14/2024)

- Pregnancy and/or lactating,
- BMI ≥ 40,
- Severe renal impairment, i.e. chronic kidney disease stages IV and V as defined by GFR < 30 ml/min/1.73 m² (21),
- Severe hepatic impairment, i.e. Child-Pugh score C⁵ (22, 23),
- Pre-existing neuromuscular disease,
- Anticipated need for postoperative intubation, and/or
- Known hypersensitivity reactions to rocuronium, neostigmine and/or sugammadex.

12. Population

We will not be including the following special populations:

- Adults unable to consent
- Individuals under the age of 18 years
- Pregnant women

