- Did not require general anesthesia for surgery,
- Did not require NMB,
- Did not receive neostigmine for NMB reversal,
- Had a TOF count < 3 or a TOF ratio ≥ 0.9 fifteen minutes after neostigmine, or
- Remained intubated in the immediate postoperative period.

As the study intervention is a one-time dose of the study drug in the OR, no further action should be required if the patient decides to later withdraw from the study. The study will be terminated when the number of participants has reached the required threshold.

17. Risk to Participants

The most common risks of sugammadex as listed by the FDA (5) include:

- Nausea (23-26%)
- Vomiting (11-15%)
- Pain (36-52%)

Uncommon but serious risks of sugammadex include:

- Hypotension (4-13%)
- Tachycardia (2-5%)

Page 12 of 30 Version: 3 (10/14/2024)

- Bradycardia (1-5%)
- Anaphylaxis (0.3%)

Notably, all of these are known to be risks of general anesthesia as well as surgery and are routinely monitored for and treated in the PACU.

18. Potential Benefits to Participants

All study subjects will have any residual NMB reversed, which will prevent any postoperative complications such as respiratory compromise or weakness.

19. Compensation to Participants

N/A

20. Data Management and Confidentiality

Data to be collected include:

- Baseline demographics: MRN, date of birth, sex (male/female), race (white, black, American Indian or Alaska Native, Asian, Native Hawaiian or Other Pacific Islander, two or more races), ethnicity (Hispanic or Latino, not Hispanic or Latino), weight (kg)
- ii. Preoperative details: ASA status (I-IV)
- iii. Surgery details: date of surgery, diagnosis, surgery, start case time (hr: min), end case time (hr: min)
- iv. Anesthesia details: if succinylcholine was used (Y/N), total amount of rocuronium given (mg), the last dose of rocuronium that was given (mg), the time that the last dose of rocuronium was given (hr:min), neostigmine dose (mg), the time that neostigmine was given (hr: min), the time that the study drug was given (hr: min).
- v. TOF ratio (0-1)
 - Before any paralytic is given at the start of the case
 - Before neostigmine is given at the end of the case
 - Before the study drug is given
 - 30 minutes after PACU arrival
- vi. TOF count (0-4 ± fade)
 - Before neostigmine is given at the end of the case
 - Before the study drug is given
- vii. The time taken to achieve a TOF ratio of 0.9 (seconds).

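### Success is defined as 95% of patients recovering, but it is judged by the confidence interval of a fitted curve, which does not measure spread between patients

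*Combined protocol and SAP*

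**What the plan says.** Section 7 (Statistical Methodology) describes the model in these terms: "an increasing exponential regression model with random intercept will be fitted with Time of Four Ratio versus Time". The equation has constants A, B and C common to all patients, one term in the log of dose, and a starting value for each patient. The only patient-level term is given one purpose: "The random intercept will allow for different initial TOFR values".

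Success is then a TOF ratio of at least 0.9 "within 5 minutes for 95% of patients, following the model estimate, adjusting for the 95% confidence intervals of the estimates". It is to be judged "based on initial TOF ratios, which may be grouped as needed".

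Two other places bear on this. Section 3 (Background) reports a dose-finding study in shallow block, where reversal was "from a TOF ratio of 0.5 to 0.9 within 5 minutes in 95% of their patients"; that is plainly a share of patients. Section 4 lists as a secondary outcome "The percentage of patients who achieve a TOF ratio of 0.9 within 1 minute, 2 minutes, 5 minutes, and 10 minutes", but nothing links the observed percentage to the success rule.

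**The concern.** A confidence interval for a fitted curve shows how well the average response is known. It does not show how far individual patients fall on either side of that average. To say that 95% of patients recover in time, the analysis must carry the between-patient spread into the decision, through a modelled percentile, a prediction or tolerance bound, or an estimated proportion. The plan names none of these.

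The model does not supply the link by itself. Its patient-level term covers different starting ratios, and the rule already conditions on starting ratio. At a given dose and starting ratio, the equation has no term for patients who recover faster or slower than one another.

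The trial's objective is an appropriate rescue dose, and its hypothesis is that less than the manufacturer's recommended dose is enough. Applied to the fitted curve, the rule could label a dose adequate for 95% of patients when the data show only that the average patient recovers in time.

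**Working it through.** **Plan's own figure.** The plan gives no error rate for this rule. Its one calculation, N = 24 for an omnibus F-test with f = 0.765, alpha 0.05 and power 0.80, reproduces with the four groups of the cited trial (power 0.82). It concerns a different question.

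**Inputs.** Threshold 0.9, time 5 minutes, target share 95% and two-sided 95% limits (Section 7, Statistical Methodology). Six patients per dose, and 1 to 3 per dose-by-twitch-count cell (Section 7, Table 1). The between-patient SD is not given, but it cancels below. Assumptions: roughly normal spread between patients at a given dose and starting ratio, and a rule that passes a dose when the lower 95% limit of the fitted curve at 5 minutes is at least 0.9.

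**Share failing at the boundary.** Let the variance of the fitted value be h × SD², and let c be the critical value. When the lower limit sits exactly at 0.9, the curve lies c√h SDs above 0.9, so the share of patients below 0.9 is Φ(−c√h).

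- One dose, 6 patients, h = 1/6. With z: 1.96/√6 = 0.80 and Φ(−0.80) = 21%. With t on 5 df: 2.571/√6 = 1.05 and Φ(−1.05) = 15%.
- Simplified straight line in ln(dose), 6 patients at each of five active doses. The doses are equally spaced on the log scale, at x = −2, −1, 0, 1, 2, so h = 1/30 + x²/60 = 0.100, 0.050, 0.033, 0.050, 0.100. The failing share runs from 26% (t on 28 df, end doses) to 36% (z, middle dose).
- Separate cells without pooling, z: Φ(−1.96/√n) = 2.5%, 8.3% and 12.9% for n = 1, 2 and 3. With t, the share is below 1% at n = 2 and 3.

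The target is 5%.

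**Chance that an inadequate dose passes.** For a dose that truly fails a share p, the curve lies z(1−p) SDs above 0.9. The chance of passing is P(T > t(0.975, df)), where T is noncentral t with noncentrality z(1−p)/√h. For p = 0.20 and n = 6 the noncentrality is 0.842 × √6 = 2.06, and P(T > 2.571) = 39%.

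| True share failing | 6 patients, one dose | Simplified pooled line |
|---|---|---|
| 10% | 71% | 97 to 100% |
| 20% | 39% | 73 to 99% |
| 30% | 18% | 36 to 79% |

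**Comparison rule.** If instead the lower 95% limit of the estimated patient share must reach 95% (same normal model, noncentral t), a dose failing 20% passes 0.3% of the time at n = 6 and less in the pooled line. A dose failing only 1% passes 9% of the time at n = 6 and 32 to 49% in the pooled line.

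**Shape check.** TOF ratio has a ceiling, so normality is doubtful. With one left-skewed shape (a reflected exponential), the n = 6 boundary share is exp(−(1 + c√h)): exp(−1.80) = 17% with z and exp(−2.05) = 13% with t.

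**The case against.** The strongest reply is that the sentence puts the 95% of patients first, so it may mean a modelled patient percentile with an allowance for estimation error. Nothing in the plan says that the limit of the mean curve is the test. This stands: the pass rates above belong to one reading, and on the other the excess is smaller or absent. The gap remains, because the plan does not say how such a percentile would be obtained.

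A reader might infer that the model holds no between-patient information at all. That goes too far. A random intercept estimated from serial readings takes up part of any difference in recovery, and otherwise that difference falls into the residual. Either variance could give an approximate percentile. The plan simply does not bring it into the rule.

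A reader might also take the pooled figures as the trial's error rates. The documents do not support that. The straight line is not the plan's exponential model, it omits uncertainty in A and B, and it ignores the Table 1 imbalance in starting state. With starting-ratio groups left open, small unpooled cells would shrink or reverse the excess.

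Finally, the primary outcome is time to 0.9, the observed 5-minute percentage is already to be reported, and a separate analysis by twitch count is planned to find an optimal dose. The success rule is therefore not the only route to a dose conclusion. This limits the consequence but does not repair the rule.

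**Conclusion.** The point holds in conditional form. The plan states a target for a share of patients and a basis for judging it that does not measure that share. Read as the confidence limit of the fitted curve, with roughly normal spread and 6 patients per dose, the rule admits doses at which about 15 to 21% of patients fail, and it passes a dose failing 20% about 39% of the time. Pooling across doses would be more lenient, with roughly 26 to 36% failing at the boundary in the simplified fit. These are boundary cases and conditional pass rates, not forecasts for this trial.

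It would be wrong to conclude that the trial's main comparison is compromised: the comparison of time to a TOF ratio of 0.9 does not use this rule. The change should be made before analysis, and it concerns the claim of adequacy for 95% of patients.

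**What to change.** - Judge success at each dose on the estimated proportion of patients with a TOF ratio of at least 0.9 by 5 minutes, given starting ratio where the data allow, with its confidence interval.
- Obtain it from a model that includes between-patient variation in recovery as well as residual variation. If a random recovery term cannot be fitted, use a patient-level bootstrap.
- Fix the starting-ratio groups before the data are seen.
- Show beside it the observed 5-minute share by dose with its exact interval.
- Claim adequacy for 95% of patients only if the lower limit supports it. Otherwise report the estimated share and its interval.

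**Cost.** This is SAP wording, with no change to dosing, procedures or sample size. The observed share needs only the time to 0.9 already listed in Section 20. The modelled share needs the serial readings that the planned model already requires; Section 6 has the ratio measured every 20 seconds. Section 20 lists the ratio at four fixed times only, so the serial readings should be added there unless the separate collection form already has them.

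The price is wide intervals. Six successes in 6 has an exact two-sided 95% lower limit of 0.025^(1/6) = 54%, and 5 in 6 has 36%. Few or no doses may support a 95% claim, and a random recovery term may be hard to fit with 1 to 3 patients per cell.

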An *a priori* power analysis was conducted using G*Power 3.1.9.4 (20). We used an ANOVA F-Test for one-way omnibus difference between groups, alpha threshold of 0.05 for rejecting the null hypothesis, statistical power of 0.80 and a "very large" effect size of 0.765 was calculated based on results from a 2013 randomized controlled trial that examined time from TOF count = 4 to TOF ratio 1.0 comparing neostigmine to three different doses of sugammadex: 0.5, 1.0, and 2.0 mg/kg (15). This gave a required sample size of N=24. This number was increased to N=36 to account for patients with poor modeling from a high starting TOFR (resulting in few data points for that patient) or incomplete recovery within the maximum ten minutes allotted. An anticipated 70% of those enrolled will become ineligible because of an initial TOFR of 90% or greater, thus not requiring any medications, so up to 120 patients may need to be recruited and screened, but only 36 will receive any treatment.

Methodology

Randomization will occur with permuted block randomization, divided into 18 groups, to ensure proportional allocation of participants in each group over time. Dose randomization will be assigned after stratifying by initial TOFC, with a set number of patients recruited for each group, as seen the table below. This ensures that patients who likely need a lower dose are more likely to receive it. Randomization will not occur until participation is assured, i.e., their TOFR is <0.90.

Table 1: Randomization plan for patients (n=36)

| Sugammadex Dose (mg/kg) → | | 0.00 | 0.125 | 0.25 | 0.50 | 1.00 | 2.00 | | | |
|---------------------------|-----------------|------|--|----------|------------|---------|---------|------|-------|----|
| Initial TOFR | Initial TOFC | Fade | placebo | | | | | | Total | |
| ≥ 0.9 | NA | NA | No treatment; track for adverse events | | | 0 | | | | |
| | | 4 | No | 3 pt | 3 pt | 2 pt | 2 pt | 1 pt | 1 pt | 12 |
| < 0.9 | 4 | Yes | 2 pt | 2 pt | 2 pt | 2 pt | 2 pt | 2 pt | 12 | |
| | 3 | NA | 1 pt | 1 pt | 2 pt | 2 pt | 3 pt | 3 pt | 12 | |
| < 0.9 | 0-2 | NA | No t | treatmen | t; track f | or adve | se even | ts | 0 | |
| Total # of Patients (pt) | | | 6 | 6 | 6 | 6 | 6 | 6 | 36 | |

Statistical Methodology

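### The rule that names an adequate dose leaves the grouping of initial TOF ratio open, so the dose named can depend on groups chosen after the data are seen

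*Combined protocol and SAP*

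**What the plan says.** Section 2 sets the objective: to find an appropriate rescue dose. The hypothesis is that less than the labelled dose is enough.

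Section 7, Statistical Methodology, gives the rule that answers it: "Success' will be defined as TOFR of ≥0.9 within 5 minutes for 95% of patients, following the model estimate". The sentence goes on with "adjusting for the 95% confidence intervals of the estimates" and ends "based on initial TOF ratios, which may be grouped as needed". The next sentence adds: "A secondary analysis will be conducted by TOFC to determine optimal dose at each TOFC level".

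Section 7, Methodology, fixes the randomisation: "Dose randomization will be assigned after stratifying by initial TOFC, with a set number of patients recruited for each group". Table 1 then lays out three TOF-count levels by six arms.

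Section 6 says that the comparison of times to a TOF ratio of 0.9 will control for "TOF count (3 twitches, 4 twitches with fade, 4 twitches without fade") and for "TOF ratio (0 to < 0.9"), both taken just before the study drug. The model in Section 7 carries the initial TOF ratio and a term in the log of dose. It has no TOF-count term.

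**The concern.** The grouping clause leaves open how many groups there are, where they are cut, what would make grouping needed, and whether it is settled before treatment codes are opened. Nothing addresses the choice among several possible groupings. An analyst who follows the plan to the letter may therefore look at the results, choose cut-points, and name the dose that meets the rule under them. The stated hypothesis favours a lower dose, so a reader of the final report could not tell whether the groups were chosen because that dose passed.

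The per-TOF-count analysis raises a different problem. Its levels are fixed in advance, so cut-points cannot be chosen there. However, the plan promises to determine a dose at each level from very little data, and such doses could be read as established.

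**Working it through.** **1. Table 1 reproduced.** From placebo to 2 mg/kg:
- TOF count 4, no fade: 3, 3, 2, 2, 1, 1 = 12
- TOF count 4, fade: 2, 2, 2, 2, 2, 2 = 12
- TOF count 3: 1, 1, 2, 2, 3, 3 = 12

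Each arm has 6 patients and the total is 36, as stated. The 18 cells comprise four of 1, ten of 2 and four of 3: 4 + 20 + 12 = 36.

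**2. What the plan fixes and what it leaves open.** The three TOF-count/fade levels are fixed at randomisation. Initial TOF-ratio groups are fixed nowhere. Section 6 lists initial TOF ratio as a control variable for the time comparison, but does not link this to the success rule.

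**3. How much freedom this leaves.** Assume, for illustration only, that cut-points fall on a 0.1 grid from 0.1 to 0.8 (8 positions).
- At most one cut: 1 + 8 = 9 groupings
- At most two cuts: 1 + 8 + 28 = 37
- Any number of cuts: 2^8 = 256

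These are counts of options, not error rates.

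**4. Whether the fixed strata can do the job.** A Section 3 footnote defines the TOF ratio as "The ratio of the fourth (T4) to the first (T1) twitch after a TOF stimulation". With a count of 3 there is no fourth twitch, so by that definition all 12 of those patients start at 0. Any cut above 0 then divides only the 24 patients with a count of 4, who are spread over the arms as 5, 5, 4, 4, 3, 3. Section 3 also puts a count of 4 with detectable fade at a ratio of 0.1 to 0.4. The strata are thus rough TOF-ratio bands already. The finer differences can be carried by initial TOF ratio as a continuous variable.

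**5. Precision at each TOF-count level.** If all n patients succeed, the exact one-sided 95% lower bound on the success probability is 0.05^(1/n). The two-sided version is 0.025^(1/n).

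| n | one-sided | two-sided |
|---|---|---|
| 1 | 5.0% | 2.5% |
| 2 | 22.4% | 15.8% |
| 3 | 36.8% | 29.2% |
| 6 (whole arm) | 60.7% | 54.1% |
| 12 (whole stratum, all doses mixed) | 77.9% | 73.5% |

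Reaching a lower bound of 95% from raw counts alone would need ln 0.05 / ln 0.95 = 58.4, so 59 of 59 (one-sided), or 72 of 72 (two-sided). If TOF-count level meant only 3 against 4 twitches, the count-4 cells would hold 3 to 5 patients. The one-sided bounds would then be 37% to 55% (0.05^(1/5) = 0.549). Section 6 and Table 1 point to three levels.

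**6. The sample size does not cover this.** The stated N = 24 reproduces as a one-way ANOVA with four groups (noncentrality 24 × 0.765² = 14.0, power 0.82). With six arms and 36 patients, power is 0.92 (noncentrality 21.1). Both figures concern an overall difference between arms, not the naming of a dose within a group.

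**The case against.** The strongest reply is that the rule is based on a model and mentions 95% intervals, so an odd grouping of a few patients need not decide it. Section 6 already controls the time comparison for both TOF count and TOF ratio, and no grouping is mentioned for that primary outcome. The per-TOF-count analysis is labelled secondary, uses pre-set levels, and could draw on all 12 patients in a stratum, or all 36, through the dose term.

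Much of this stands, and it rules out several stronger readings:

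- A reader might infer that an inadequate low dose would readily pass in some subgroup, for example by counting cells in which every patient happens to succeed. The plan does not use raw counts. Such a calculation on Table 1 would also describe the fixed strata, which the fix keeps, and not the effect of free cut-points.
- A reader might blame regrouping for the thin cells, such as the single patients at the two top doses in the no-fade row. Those cells are planned in Table 1.
- A reader might infer that each cell of 1 to 3 patients will be analysed alone. The plan does not say so. It also does not say that a pooled model will be used, and the written model has no TOF-count term.
- A reader might try to simulate how often the named dose changes with the grouping. The result would rest on an assumed dose slope, residual spread and distribution of initial TOF ratios, and on whether the model is refitted in each group. The documents give none of these.

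The interval adjustment does not close the gap, because the plan does not say which bound is used or how it enters the rule. It is also fair to object that the plan treats the correlation between TOF count and TOF ratio as a question still to be studied. That is a reason to keep initial TOF ratio in the model as a continuous variable, not a reason to leave its grouping open.

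**Conclusion.** The concern holds for the grouping clause. The one rule that answers the primary objective permits initial TOF-ratio groups to be formed with no limit on number, position or timing, so the dose named adequate can depend on a choice made after the data are seen. That follows from the text alone. How often it would change the answer is not known from the documents, and no figure is claimed.

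For the TOF-count analysis, the conclusion is narrower: the levels are pre-set, but the wording promises more than the data can give. The 5%, 22% and 37% bounds apply to cells taken on their own with every patient succeeding. A pooled model would do better, by an amount that depends on its assumptions.

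The change should be made. It is a matter of wording and does not call the randomisation or the time comparison into question.

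**What to change.** In Section 7, Statistical Methodology:

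1. Delete the permission to group from "based on initial TOF ratios, which may be grouped as needed".
2. State that one model is fitted to all patients, with initial TOF ratio as a continuous covariate and the randomised stratum (count 4 without fade, count 4 with fade, count 3) as a term. The stratum term is needed because initial TOF ratio does not vary among the count-3 patients. The written dose term is a logarithm and is undefined at zero, so the text must also say how placebo patients enter.
3. Judge success from that model in the three randomised strata. Say in advance at which initial TOF ratios the prediction is evaluated, for example averaged over the stratum's 12 patients.
4. Report any other grouping as post hoc.
5. In "A secondary analysis will be conducted by TOFC to determine optimal dose at each TOFC level", replace the promise to determine a dose with one to estimate it, as exploratory, with intervals, from the same pooled model.

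Make the change before treatment codes are opened. If that time has passed, label any initial TOF-ratio grouping as post hoc in the report.

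The cost is SAP wording only: no added patients, procedures or dosing changes. The downside is that the investigators give up later regrouping as part of the planned rule and make a more modest claim for the per-level doses.
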